9.4.2.2. Renal-Related Outcomes

The following renal-related outcomes will be reported as both incidence proportions and exposure-adjusted incidence rates:

- Incidence of sCr elevation ($\geq 1.5 \times$ Baseline).
- Incidence of subjects meeting criteria (eg, based on sCr or eCrCl criteria) for treatment discontinuations.
- Incidences of renal-related and kidney stone TEAEs and SAEs.
- Prevalence of contributing factors to renal SAEs as adjudicated by the REAC.

The proportion will be calculated as the number of subjects with an outcome of interest (ie, unique subjects) during the study divided by the total number of subjects in that treatment group. The 95% CIs will be calculated based on the Wilson Score method.

The on-treatment exposure-adjusted incidence rates for an outcome of interest will be calculated as the number of subjects with that outcome of interest during the Treatment Period divided by the total duration of treatment in each treatment group (ie, “on-treatment” analysis). Similarly, the on-study exposure-adjusted incidence rates will be calculated as the number of subjects with outcome of interest during the study divided by the total duration of study in each treatment group (ie, “on-study” analysis). Exposure-adjusted incidence rates and associated exact CIs

based on the Poisson distribution will be calculated for each treatment group and reported per 100 patient-years.

Similar exposure-adjusted analysis will also be performed with the number of events as the numerator dividing by on-treatment or on-study exposure as described above.

Estimates of treatment differences with corresponding 95% CIs will be calculated. The appropriate approaches may depend on the number of events observed during blinded data review and will be detailed in the SAP prior to database lock.

Additional assessments may include the proportion of subjects who require dialysis, those who advance in their chronic kidney disease, those who have persistent decreases in eCrCl, and those who have persistent sCr elevations.

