A detailed analysis of renal safety in the pivotal Phase 3 combination therapy studies showed that lesinurad was associated with transient increases in serum creatinine (sCr). These sCr elevations generally resolved, most without treatment interruption. The incidence of renal-related serious TEAEs was low ($\leq 1\%$), and the exposure-adjusted rates were not increased following long-term exposure during the extension studies.

In the pivotal Phase 3 combination therapy studies, overall rates of adjudicated Major Adverse CV Events (MACE) and of Investigator-reported CV-related AEs, AEs leading to discontinuation of IP, and serious AEs (SAEs) were low. The incidence of MACE was comparable for lesinurad 200 mg in combination with an XOI (4 subjects) and XOI alone (3 subjects). The small number of MACE observed in the pooled analysis of data from the pivotal Phase 3 combination therapy studies places limitations on assessment of treatment-associated differences in MACE risk.

Refer to the lesinurad [Investigator's Brochure](#) (IB) for more information on lesinurad.

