8.3. Treatment Period (Day 1 Through Month 24)

Subjects must meet all of the eligibility criteria listed in [Section 4.2](#) and [Section 4.3](#) before being randomized and starting IP, study-supplied XOI, and colchicine (as applicable). Subjects will receive IP in combination with an XOI for up to 24 months. Subjects who permanently discontinue IP early should complete an End of Treatment Visit ([Section 8.3.3](#)) as soon as possible after discontinuing IP, and a Post-End of Treatment Visit ([Section 8.4.1](#)) 1 month after the End of Treatment Visit, but should remain on the study and follow the protocol-scheduled visits.

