9.4.2.3. Cardiovascular Outcomes

The following cardiovascular outcomes will be reported as both incidence proportions and exposure-adjusted incidence rates:

- Incidence of CEAC-adjudicated MACE (CV death, nonfatal myocardial infarction, and nonfatal stroke).
- Incidence of CEAC-adjudicated MACE or hospitalization for unstable angina (MACE+).

Similar methods for estimating incidence proportions and exposure-adjusted incidence rates will be applied, as described in [Section 9.4.2.2](#). In addition, the incidences of the individual MACE+ components will also be reported.

In addition, the time-to-event of MACE will be analyzed using Cox proportional hazards model with treatment as the only predictor (base model). The estimated hazard ratio and associated 95% CI will be presented. Extended models (eg, including stratification factors, other Baseline covariates, etc.) may be explored depending on the number of events observed.

Two types of analyses will be conducted: on-study analysis and on-treatment analysis. For the on-study analysis, subjects with an event during the study will contribute actual time of first occurrence, while those without an event will be censored at the end of study. For the on-treatment analysis, subjects with an event during the Treatment Period will contribute actual time of first occurrence, while those without an event during Treatment Period will be censored at the end of treatment. Sensitivity analysis may be conducted to explore different ascertainment windows for which to attribute the MACE outcome to treatment (eg, 1 month post-treatment discontinuation).

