9.4.2.4. General Safety

All AEs will be coded and tabulated by Medical Dictionary for Regulatory Activities (MedDRA) System Organ Class and preferred term. Similar methods will be applied for estimating proportions and exposure-adjusted incidence rates (ie, on-study and on-treatment exposure-adjustment) of TEAE, SAEs, and TEAEs leading to permanent discontinuation of IP, as described in [Section 9.4.2.2](#).

Associated laboratory parameters such as hepatic profile, renal function, serum chemistry, hematology, and urinalysis values will be grouped and presented together. Individual subject values will be listed and values outside of the standard reference range will be flagged. Marked abnormalities meeting RCTC version 2.0 grading will also be noted. Shift tables and analyses of changes from Baseline will be included.

The change from Baseline for each of the vital signs variables will be summarized.

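### Subject-based exposure-adjusted rates keep time after the first event in the denominator, which understates first-event rates for the commoner outcomes

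*Combined protocol and SAP*

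**What the plan says.** Section 9.4.2.2 of the protocol reports renal outcomes as incidence proportions, counting unique subjects, and as exposure-adjusted rates per 100 patient-years with exact Poisson intervals. The on-treatment rate is "the number of subjects with that outcome of interest during the Treatment Period divided by the total duration of treatment in each treatment group". The on-study rate is the "number of subjects with outcome of interest during the study divided by the total duration of study in each treatment group". Neither definition stops a subject's time at the first event.

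The section then adds a second kind of rate: "Similar exposure-adjusted analysis will also be performed with the number of events as the numerator", over the same exposure. It also commits to comparison between arms: "Estimates of treatment differences with corresponding 95% CIs will be calculated". The SAP is left to choose the approach to those differences; the definition of the rate itself is not deferred.

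Section 9.4.2.3 applies similar methods to MACE and MACE+. Section 9.4.2.4 does so for TEAEs, SAEs and TEAEs leading to permanent discontinuation: "Similar methods will be applied for estimating proportions and exposure-adjusted incidence rates". Only the Cox model for MACE in Section 9.4.2.3 uses time to first event; in its on-study form, "subjects with an event during the study will contribute actual time of first occurrence".

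**The concern.** A subject who has had the outcome can no longer add to a numerator that counts each subject once, yet that subject's later time still enlarges the denominator. With complete follow-up the rate is just the incidence proportion divided by a constant, so the on-study rate adds no timing information to the proportion already reported.

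Post-event time will accrue here. Section 1.2.1 says that most Phase 3 creatinine elevations resolved without treatment being interrupted, Section 6.12.1 encourages keeping subjects on investigational product (IP) during retesting, and Section 5.3.2.1.2 asks subjects who stop IP to stay on study. Creatinine of at least 1.5 times Baseline is a listed safety endpoint in a trial whose primary objective is safety.

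If post-event exposure is similar in the two arms, the arm with more events gains more surplus time. The ratio and the difference in rates are then both pulled towards no difference, which is the unhelpful direction for a safety comparison.

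**Working it through.** The plan gives no numerical exposure-adjusted rate, so there is no stated figure to reproduce.

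**Inputs.** Treatment lasts 24 months (Section 3.1) of 28 days each (Section 8), so T = 24 × 28 / 365.25 = 1.84 years. Planned group size is 300 (Section 4.1). Incidence p is assumed at 1%, 5%, 10% and 20%. The base case has a constant hazard, full follow-up and exposure that continues after the event.

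**Size within one arm.** Planned rate = p/T. First-event rate h = −ln(1 − p)/T. Their ratio, p/(−ln(1 − p)), does not depend on T.

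| p | Planned, per 100 PY | First-event, per 100 PY | Understated by |
|---|---|---|---|
| 1% | 0.544 | 0.546 | 0.5% |
| 5% | 2.72 | 2.79 | 2.5% |
| 10% | 5.44 | 5.73 | 5.1% |
| 20% | 10.87 | 12.13 | 10.4% |

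**Size for the comparison, true rate ratio 2.0.** Lesinurad incidence is p1 = 1 − (1 − p0)². The planned ratio is p1/p0, the risk ratio. The true difference is 2h − h = h, and the planned difference is (p1 − p0)/T.

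| p0 | p1 | Planned ratio | True difference, per 100 PY | Planned difference | Shrinkage |
|---|---|---|---|---|---|
| 1% | 1.99% | 1.99 | 0.55 | 0.54 | 1.5% |
| 5% | 9.75% | 1.95 | 2.79 | 2.58 | 7% |
| 10% | 19% | 1.90 | 5.73 | 4.89 | 15% |
| 20% | 36% | 1.80 | 12.13 | 8.70 | 28% |

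**Event timing.** If events fall on average at fraction u of follow-up, the understatement is p(1 − u). For u = 0.10, 0.50 and 0.75 this is 9%, 5% and 2.5% at p = 10%, and 18%, 10% and 5% at p = 20%.

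**Dropout.** Simulation with an assumed 20% to 40% dropout over 24 months gives 5.5% to 6.0% at p = 10%, and 11.1% to 12.2% at p = 20%.

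**Events that stop IP (on-treatment rate).** If a share q of subjects with events stop IP at the event, mean exposure is (1 − q)T + q·p/h. With no dropout and q = 0.5, the understatement falls to 2.6% at p = 10% and 5.5% at p = 20%; with q = 1 it is zero. At p0 = 10% and a true ratio of 2.0:

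| q placebo | q lesinurad | Planned ratio |
|---|---|---|
| 0 | 0 | 1.90 |
| 0.5 | 0.5 | 1.95 |
| 0 | 0.5 | 2.00 |
| 0 | 1 | 2.11 |
| 1 | 1 | 2.00 |

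**Against sampling error.** Person-time per arm is 300 × 1.84 = 552 PY. At 10% versus 19% there are 30 and 57 subjects with events, so the approximate 95% half-width of the rate difference is 1.96 × √(30 + 57)/552 = 3.3 per 100 PY. The shift is 5.73 − 4.89 = 0.84, about a quarter of that. At 20% versus 36% (60 and 108 subjects) the half-width is 1.96 × √168/552 = 4.6 and the shift is 12.13 − 8.70 = 3.43, about three quarters.

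**The case against.** The strongest reply is that the plan defines its quantity openly and never calls it a hazard or a first-event rate, so nothing is understated on its own terms. The same outcomes are also reported as proportions and event-count rates, MACE has a Cox model that stops at the first event, and Section 9.4.2 makes safety analysis descriptive. No test, margin or stopping rule rests on these rates. With 30 events the exact Poisson interval runs from about 20.2 to 42.8 events, −33% to +43%, beside a 5% shift.

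Much of this stands as a limit on importance. Section 1.2.1 reports of Phase 3 that "The incidence of renal-related serious TEAEs was low", at or below 1%, where the effect vanishes. The documents give no incidence for creatinine elevation, so whether it reaches 10% is unknown. The direction is not fixed on treatment: unequal stopping of IP can cancel or reverse the shift. The section does not say whether its treatment differences concern proportions, rates or both, so applying the shrinkage to rate differences is an inference. The rate does adjust for unequal follow-up, so it repeats the proportion only when follow-up is complete.

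The estimand argument does not stand. Total exposure is the natural denominator for the event-count rate, which is planned separately. Over the same exposure, the subject-based rate counts time in which a subject cannot contribute a first event. The plan already stops the clock at first occurrence, but only for MACE, where it matters least.

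**Conclusion.** The concern holds. Followed as written, the definition understates first-event rates by about 5% at 10% incidence and 10% at 20%. Where post-event exposure is similar between arms, it also draws comparisons towards no difference. These figures rest on assumed incidences, a roughly constant hazard, full follow-up and exposure that continues after the event. Earlier events enlarge the effect, up to p itself; later events, or events that end treatment, reduce it. It is negligible for MACE and renal serious events, absent from the on-treatment rate of TEAEs leading to permanent discontinuation, and does not touch the main eCrCl analyses. It should be corrected before database lock because the change is cheap and the definition governs all the renal, cardiovascular and adverse-event rates.

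**What to change.** In Section 9.4.2.2, state that for rates counting subjects, person-time runs from first dose to the first occurrence of that outcome, or to the end of treatment or study if there is none. Keep total exposure for event-count rates only. Sections 9.4.2.3 and 9.4.2.4 inherit the change by reference.

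As a clarification only, state one on-treatment window and use it for the numerator, the denominator and the on-treatment Cox censoring. Section 8.3 heads the Treatment Period as Day 1 to Month 24, while Section 8.3.3 separates completing it from stopping IP early. Time on IP is the likely intent.

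The cost is one or two sentences and no new data: adverse-event start dates and dated central-laboratory creatinine are already collected. Each outcome, including each MedDRA term, will need its own denominator. Creatinine onset is seen only at visits, mostly three months apart, or at retests, so its first-event time will be approximate.

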4. STUDY POPULATION SELECTION

4.1. Study Population

Approximately 600 subjects will be enrolled (300 per treatment group).

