9.1. General Considerations

All subjects will be randomized to either lesinurad 200 mg or matching placebo in combination with an XOI in a 1:1 ratio and stratified by the following stratification factors:

- Screening eCrCl: the average eCrCl of Screening Visit 1 and Screening Visit 2 (30.0 to <45.0 mL/min or 45.0 to <60.0 mL/min).
- Baseline measurable target tophus status: present or absent.
- Type of XOI: allopurinol or febuxostat.

This study will enroll approximately 50% of subjects with eCrCl 30.0 to <45.0 mL/min and approximately 50% with eCrCl 45.0 to <60.0 mL/min. There is no planned sample size requirement on the number of subjects enrolled by type of XOI or Baseline tophus status. However, a stratification variable (eg, Baseline measurable target tophus status [present/absent]) may be dropped from the stratified analysis (eg, mixed model repeated measures [MMRM] or Cochran Mantel Haenszel [CMH]) if the number of subjects in any stratum is very low (eg, <10% of total subjects). The decision to drop a stratification variable will be made prior to database lock and will be documented in the SAP.

All safety and efficacy data will be listed and summarized by treatment group.

Baseline is defined as the last observed measurement prior to the first dose of IP, unless otherwise specified.

Descriptive statistics will consist of the number of subjects (n), mean, standard deviation (SD), median, minimum, and maximum for continuous variables, and counts and percentages for categorical variables.

Unless otherwise specified, all confidence intervals (CIs) will be calculated at the 95% level and all hypothesis tests will be performed at the 0.05 level. All analyses including summaries and listings will be performed using SAS[®] software version 9.1 or higher.

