9.2. Determination of Sample Size

Approximately 600 subjects will be randomized 1:1 to either the lesinurad (LESU) + XOI or placebo (PBO) + XOI group in this study.

For safety endpoint analyses, this sample size provides sufficient precision around the estimated between-treatment difference for the absolute and percent changes in eCrCl from Baseline to Month 24 based on the normal distribution CI with 95% two-sided confidence level. For the difference in absolute change from Baseline to Month 24, the estimated precision is ± 1.6 mL/min assuming a common SD for the change from Baseline in each treatment group of 10 mL/min estimated from the lesinurad Phase 3 development program. For the difference in percent change from Baseline to Month 24, the estimated precision is $\pm 3.2\%$ assuming a common SD for the

percent change from Baseline in each treatment group of 20% estimated from the lesinurad Phase 3 development program.

For the key efficacy endpoint analyses, this sample size will provide >90% power for the overall population and >80% power within each Screening eCrCl stratum to detect a treatment difference for the proportion of subjects achieving sUA <6.0 mg/dL at Month 6 of 15% (20% in the PBO + XOI group versus 35% in the LESU + XOI group, as estimated from the lesinurad Phase 3 development program), using a binomial distribution at an alpha of 0.05 (two-sided). Based on the assumptions above, this sample size provides sufficient precision such that the minimum statistically significant difference in response rate is approximately 10% in the overall population, and approximately 11% in the Screening eCrCl 30.0 to <45.0 mL/min stratum, at the two-sided 5% level.

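### Renal events are specified only as proportions and constant-rate incidence; the on-treatment rate can differ between arms of equal risk, and no time-to-event analysis is specified outside MACE

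*Combined protocol and SAP*

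**What the plan says.** Section 9.4.2.2 covers serum creatinine (sCr) at or above 1.5 times Baseline, subjects meeting discontinuation criteria, renal-related and kidney stone TEAEs and SAEs, and adjudicated contributing factors. Each is reported in two forms:

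- a crude proportion over all subjects in the arm, counting outcomes during the study, with a Wilson interval;
- an exposure-adjusted rate per 100 patient-years with an exact Poisson interval.

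The on-treatment rate takes subjects with the outcome in the Treatment Period "divided by the total duration of treatment in each treatment group"; the on-study rate uses study duration in the same way. Event-count versions are also planned. Treatment differences with 95% CIs are promised, but the method may depend on event counts seen at blinded review and is deferred to the SAP.

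Section 9.4.2.3 goes further for cardiovascular outcomes: "the time-to-event of MACE will be analyzed using Cox proportional hazards model", with treatment as the only predictor and with on-study and on-treatment censoring rules.

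Section 9.4.2 names the absolute and percent change in eCrCl to Month 24, analysed by MMRM, as the main safety estimands. On the behaviour of creatinine, Section 1.2.1 says that "lesinurad was associated with transient increases in serum creatinine (sCr"), without giving their timing.

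**The concern.** Dividing subjects with an event by person-time treats every month on drug as equally risky. If most first creatinine elevations come soon after the first dose, the later months add time to the denominator and few events to the numerator. An arm whose subjects stop IP sooner loses mainly that quiet late time, so its rate rises although its risk is the same.

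Renal safety is the stated focus of the study (Section 1.3), and the safety data are to be read descriptively (Section 9.4.2), so the estimate and its interval are the result. A rate ratio that partly reflects stopping patterns would be read as a renal effect. Nothing specified for renal events shows when they occur, although the plan already has the machinery for MACE.

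**Working it through.** **The plan's own figures.** Section 9.4.2.2 states none. The nearest are in Section 9.2, and they reproduce with 300 per arm:

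- eCrCl precision, "assuming a common SD for the change from Baseline in each treatment group of 10 mL/min": 1.96 × 10 × √(2/300) = 1.60 mL/min (stated ±1.6). With SD 20%: 3.20% (stated ±3.2%).
- Power for 20% vs 35%: 98.6% with 300 per arm and 83.2% with 150 (stated >90% and >80%).

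**Inputs from the documents.** 300 per arm (Section 4.1). 24 months of 28 days (Sections 3.1 and 8), so T = 672/365.25 = 1.84 years. On-treatment rate as defined in Section 9.4.2.2.

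**Assumed inputs (not in the documents).** True risk of a first event by Month 24, F = 10% in both arms (range 5% to 20%). Share f of the cumulative hazard in the first 3 months: 50% or 80% (also 50% or 70% in the first 6 months). IP stopping by Month 24, s = 20% in one arm and 30% to 50% in the other, at a constant stopping hazard.

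**Formulas.**

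- Cumulative hazard H = −ln(1 − F) = 0.105 at F = 10%; stopping hazard g = −ln(1 − s)/T.
- Mean treatment time = s/g. For s = 20%: 1.84 × 0.20/0.2231 = 1.649 years. For s = 40%: 1.84 × 0.40/0.5108 = 1.441 years.
- Early period a = 84/365.25 = 0.230 years; h1 = fH/a; h2 = (1 − f)H/(T − a).
- Probability of an on-treatment event: P = h1/(h1+g) × [1 − e^(−(h1+g)a)] + e^(−(h1+g)a) × h2/(h2+g) × [1 − e^(−(h2+g)(T−a))].
- Rate = 100 × P / mean treatment time.

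**Results, F = 10%, stopping 20% vs 40%.**

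| Hazard in first 3 months | P, 20% stop | P, 40% stop | Rate, 20% stop | Rate, 40% stop | Ratio |
|---|---|---|---|---|---|
| 12.5% (constant hazard) | 8.98% | 7.87% | 5.45 | 5.46 | 1.00 |
| 50% | 9.37% | 8.66% | 5.68 | 6.01 | 1.06 |
| 80% | 9.67% | 9.29% | 5.86 | 6.45 | 1.10 |

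Over all the assumed values of F and f, the ratio is 1.02 to 1.05 for 30% vs 20% stopping, 1.04 to 1.10 for 40% vs 20%, and 1.06 to 1.17 for 50% vs 20%. With a constant hazard it stays at 1.00 to 1.01, so front-loading drives the effect. Cutting person-time at the first event barely changes it (1.098 instead of 1.099 in the last row), so the denominator definition is not the cause.

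**Size against sampling error.** The last row means about 27.9 vs 29.0 events with 300 per arm. The SE of the log ratio is √(1/27.9 + 1/29.0) = 0.265, so a ratio of 1.10 carries a 95% CI of about 0.65 to 1.85.

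**Simulation.** 3,000 trials per scenario, 300 per arm, no true difference. With front-loaded events and 20% vs 40% stopping:

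- the on-treatment rate ratio averaged 1.04 to 1.10, and its 95% CI excluded 1 in 3% to 6% of trials;
- the on-study rate ratio, with complete off-IP follow-up, was 0.995 to 1.00.

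Across all scenarios, including equal stopping and constant hazard, a time-to-event analysis censored at IP stop gave a mean hazard ratio of 0.99 to 1.00, with log-rank rejection of 4.8% to 5.6%.

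**A different premise: unequal withdrawal from the study.** With 25% vs 10% withdrawing and F = 10%, the proportion ratio is 0.92 to 0.97 and the on-study rate ratio 1.00 to 1.06.

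**The case against.** The strongest case on the other side has five parts.

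- **The between-arm method is open.** A reader might infer that renal arms will be compared only by proportions and rates. The text does not support that: Section 9.4.2.2 defers the method to the SAP, and the combined document holds no separate SAP text on it. What stands is that nothing specified commits to a time-to-event analysis.
- **An undistorted companion is planned.** The proportion counts outcomes during the study, and every on-treatment rate has an on-study partner. Subjects who stop IP are asked to stay, with AEs and creatinine as the minimum (Section 5.3.2.1.2). This largely stands. It weakens where follow-up becomes telephone contact or one contact at Month 24, which the same section allows: study time can then accrue without creatinine values. It also means that the planned proportion and rate cannot be said to point in opposite directions because of IP stopping. That contrast needs an on-treatment proportion, which is not planned.
- **Renal events are not the main estimand.** Correct. Mean eCrCl by MMRM is, and its treatment-by-visit term handles time course. It does not describe the incidence of creatinine elevations, renal AEs or stones.
- **Both driving conditions are assumed.** Correct. Transient does not mean early, and Section 1.2.1 adds that most elevations resolved without interruption. Section 6.12 encourages keeping subjects on IP during retesting. Yet Section 9.4.2.1 itself foresees early discontinuation for worsening renal function, so unequal stopping is plausible.
- **Events may be too few for modelling.** This stands for SAEs. Section 1.2.1 puts renal-related serious TEAEs at 1% or less in Phase 3, or about 3 per arm if carried over (0.01 × 300). A Cox model over the 2 × 2 × 2 = 8 randomisation strata could not be supported.

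**Conclusion.** The point holds as a modest gap in specification. The on-treatment exposure-adjusted rate is a fair between-arm summary only under a roughly constant hazard. If events are front-loaded and IP stopping differs, it overstates the rate in the arm that stops more, by about 2% to 17% over the range examined; with 80% of the hazard in the first 3 months, by about 4% to 10% for 30% to 40% vs 20% stopping. All of this rests on assumed timing and stopping.

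A reader might infer inflated false positives. For the planned total-duration rate the documents' design does not bear this out: intervals excluded 1 in 3% to 6% of null trials. Rejection of 6% to 10% arose only in a variant that cuts time at the first event, which the plan does not use. The main safety estimand and the on-study summaries are not undermined. The case for change is that a better description of renal events is available at little cost.

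**What to change.** In Section 9.4.2.2 (and the SAP), add a time-to-first-event analysis for sCr at or above 1.5 times Baseline and for the first renal-related or kidney stone TEAE, using the on-study and on-treatment censoring rules of Section 9.4.2.3:

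- cumulative incidence to Month 24 by arm, with death as a competing event;
- the difference between arms with a 95% CI;
- a Cox hazard ratio with treatment as the only predictor, as for MACE, adding stratification factors only if event counts allow.

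For renal SAEs, show cumulative incidence descriptively if events are few. Keep proportions and exposure-adjusted rates as descriptive summaries.

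Cost: some wording and a few more tables and curves; no new data, since laboratory, AE and dosing dates are already collected. Two limits should be stated. Creatinine event times will be coarse, because visits are mostly 3-monthly. The on-treatment version still assumes that stopping IP is unrelated to later risk, so it should be presented beside the on-study version.
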